10.2. Treatment Allocation

All trial participants will receive radiotherapy.

Participants will be allocated between the three groups – control, test group 1 and test group 2 - on a 1:1:1 basis (open-label). Allocation will be by computer generated random permuted blocks. Randomisation will be stratified by:

- breast surgery type (breast conservation surgery (including mammoplasty) or breast conservation surgery with perforator flap reconstruction)
- need for nodal radiotherapy (none, nodes not including IMC or nodes including IMC)
- treating centre.

10.3. Endpoint Definitions

Primary endpoint

The primary endpoint is ipsilateral breast tumour recurrence at 5 years, defined as either invasive or non-invasive ipsilateral tumour recurrence in the breast, including tumours considered to be new primaries by virtue of biology or location. Kaplan-Meier estimation will be used, with observations censored at death or most recent follow-up assessment for those patients without an event.

Secondary endpoints

- Patient-reported acute radiotherapy adverse effects (up to 3 months post-treatment*), with a focus on skin, breast, and oesophageal toxicity (PRO-CTCAE v5.0 and trial-specific assessments).
- Patient-reported late effects (between 1- and 5-years post-treatment*), with a focus on breast and arm/shoulder symptoms, using both standard instruments (EORTC QLQ BR-23) and trial-specific assessments.
- Patient-reported fatigue and quality of life (EORTC QLQ FA12, QLQ C30, QLQ BR-23, Body Image Scale (BIS), EQ5D-5L), measured throughout follow-up.
- Clinician-reported acute skin and oesophageal toxicity (CTCAE v5.0, up to 7 weeks post-treatment*) and breast oedema (trial specific, used in previous trials).
- Clinician-reported lung toxicity (RTOG, 3- and 12-months post-treatment*).
- Clinician-reported late normal tissue effects and cosmetic outcome (between 1- and 5-years post-treatment*), assessed with tools developed in previous breast radiotherapy trials and the Harvard Harris scale.

- Clinician-reported other late radiotherapy adverse events (between 1- and 5-years post-treatment*), including arm and breast lymphoedema, sensori-motor symptoms, symptomatic rib fracture, symptomatic lung fibrosis and ischaemic heart disease.
- Recurrence-free survival, defined as time to the first of: invasive ipsilateral breast tumour recurrence, invasive loco-regional recurrence, distant recurrence or death from any cause. Observations will be censored at most recent follow-up assessment for those patients without an event.
- Breast cancer-related survival, defined as time to breast cancer death. Observations will be censored at death due to other cause or most recent follow-up in those patients without an event.
- Overall survival, defined as time to death from any cause, with observations censored at most recent follow-up for surviving patients.
- Cost-effectiveness, based on health economic analysis which incorporates data on patient-reported health resource usage and health status (EQ-5D-5L).

**Follow-up times are measured from treatment start date.*

10.4. Statistical Analysis Plan

Statistical analyses will be conducted at the ICR-CTSU. Analysis details are outlined here in brief. Full details will be specified in a Statistical Analysis Plan in accordance with ICR-CTSU Standard Operating Procedures. Health economics analysis will be conducted by the University of York and detailed in a separate analysis plan (Appendix A3 provides further details of the health economic evaluation).

Timing of the analyses

Subject to guidance from the IDMC, the primary analysis is expected to take place when all patients have completed a minimum of 4 years follow-up in the trial (or are known to have been lost to follow-up or withdrawn), with a median follow-up time of approximately 5 years. A later analysis, incorporating routinely collected healthcare data (subject to validation), will focus on long-term cancer outcomes.

Some secondary endpoint data will mature whilst the trial is ongoing and it is intended that results from these analyses will be published ahead of primary endpoint data, to provide reassurance of the safety of the 5Fr approach. These include:

- Early side effects sub-study analysis, including acute toxicity and dosimetry data (103 patients in each test group with relevant CTCAE v5.0 data)
- Subgroup analysis of pneumonitis rates in IMC population (including at least 311 patients receiving IMC radiotherapy in either test group with relevant 3-month RTOG data)
- Late normal tissue effects analysis (including 823 patients in each trial arm with the relevant 3-year data on breast induration)

Analysis sets

Primary efficacy analyses will be based on the intention-to-treat analysis set (including all patients according to allocated trial arm). However, given the non-inferiority hypothesis, sensitivity analysis based on a per protocol analysis set will also be conducted to consider the impact of non-compliance and draw robust conclusions about non-inferiority. Safety analyses will be based on a per protocol analysis set, according to treatment received. Full definitions of the analysis sets will be provided in the analysis plan.

Analysis of the primary endpoint

The primary endpoint will be presented by trial arm using Kaplan-Meier curves; estimated 5-year event rates will be given along with 95% confidence intervals. The treatment effect from each pairwise comparison will be presented as an absolute difference, by applying the hazard ratio (and corresponding 95% confidence interval) to the control group 5-year event-free estimate. This will be the primary assessment of non-inferiority (whether or not the upper limit of the confidence interval exceeds 2%). Additionally, the hazard ratio will be used to present treatment effect on a relative scale, presented with a 95% confidence interval. Hazard ratios will be derived from Cox proportional hazard regression models. The primary analysis will be unadjusted, but estimates will also be presented after adjustment for factors used in the randomisation algorithm and other important prognostic factors (which will be pre-specified in the analysis plan). As noted above, a sensitivity analysis based on a per protocol population will also be reported. The proportional hazards assumption will be checked and, if violated, appropriate alternative methods will be applied.

Analysis of secondary endpoints

PRO questionnaires will be scored using published manuals, including methods for handling missing data. Analyses of both patient-reported and clinician-reported toxicity data will follow methods established in previous breast radiotherapy trials(6, 10, 16, 39, 40) (11) and will account for multiple testing by adjustment of significance levels. Frequencies of early and late toxicities will be summarised at each time point/period and compared between treatment groups using chi-squared test or Fisher's exact test as appropriate. Where appropriate, longitudinal models (e.g. generalised estimating equations) including all assessments over follow-up, and survival analyses of time to first moderate/marked adverse effect will be carried out with comparisons between treatment groups, adjusting for balancing and other factors (for example, pre-treatment HADS score) where relevant. Event rates at key time points will be reported with 95% confidence intervals. For the analysis of late radiation effects on normal tissues the two test groups will be compared to estimate by interpolation the 5Fr schedule equivalent to control in terms of adverse effects.

For the early side effects sub-study analysis, dosimetry data will be summarised descriptively to support interpretation of acute toxicity data.

Recurrence-free survival, breast cancer-related survival and overall survival will be analysed in a similar way to the primary endpoint. However, particularly for breast cancer-related and overall survival, analyses are likely to be largely descriptive due to the rarity of events which may preclude formal statistical comparisons.

Use of routinely collected healthcare datasets

Data on cancer events and deaths reported via routinely collected healthcare datasets, where available, will be obtained over a 10-year follow-up period. An initial snapshot of this data will cover the primary analysis period (when all patients have been followed up for 5 years) and the aim of this complementary analysis will be to explore ascertainment of the primary endpoint events (ipsilateral breast tumour recurrence) within these datasets when compared with trial-specific reporting. Depending on the results of this analysis, a 10-year analysis based on routinely collected data is planned which would provide updated data on the primary endpoint and other cancer outcomes.

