Timing of assessments (assuming no treatment interruptions*):

	Control Group	Test Group
Week 1	At fraction 5	At fraction 5
Week 2	At fraction 10	7 days after final fraction
Week 3	At fraction 15	14 days after final fraction
Week 4	7 days after final fraction	21 days after final fraction
Week 5	14 days after final fraction	28 days after final fraction
Week 6	21 days after final fraction	35 days after final fraction
Week 7	28 days after final fraction	42 days after final fraction

*In the unlikely event of treatment interruptions, the timing of these weekly assessments should remain scheduled in accordance with the originally planned start and end dates.

Month 3

The following assessments should be conducted at 3 months after the start of radiotherapy for all participants:

- Lung toxicity assessment (RTOG) (*can be conducted by remote consultation*)
- Participants who have consented to complete PRO questionnaires will be sent/given a Follow-up (e)PRO booklet, including the following questionnaires (*for UK participants this will be coordinated by ICR-CTSU*):
 - EORTC QLQ-C30 and QLQ-BR23
 - Body Image Scale (BIS)
 - Fatigue (EORTC QLQ FA12)
 - EQ-5D-5L

- Radiotherapy symptoms (breast & arm/shoulder trial specific, used in previous trials).
- Patient reported health care resource use (UK only)

Additional assessments at month 3 for EARLY SIDE-EFFECTS SUB-STUDY ONLY

Patients will be sent the sub study specific “Follow Up Assessments – 3 months” (e)PRO booklet, containing the following additional questionnaires (*this will be coordinated by ICR-CTSU*):

- Patient assessed skin, breast, and oesophageal toxicity assessment (PRO-CTCAE V5.0 and trial specific questions as used in previous trials).

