9. SAFETY REPORTING

9.1. Definitions

Adverse Event (AE)

An AE is any untoward medical occurrence in a patient administered a study treatment; the event does not necessarily have a causal relationship with the treatment.

Serious Adverse Event (SAE)

An SAE is any untoward medical occurrence that occurs after the first radiotherapy treatment and within 30 days of the last treatment of radiotherapy and

- results in death,
- is life-threatening,
- requires hospitalisation or prolongation of existing inpatients' hospitalisation,
- results in persistent or significant disability or incapacity,
- is a congenital anomaly or birth defect.

Important adverse events that are not immediately life-threatening or do not result in death or hospitalisation but may jeopardise the subject or may require intervention to prevent one of the other outcomes listed in the definition above, may also be considered serious.

Progression of the indicated disease and death due to progression of the indicated disease are not considered SAEs and do not need to be reported as such but should be reported on the appropriate eCRF as required.

Pregnancy or aid in the conception of a child whilst participating in a trial is not itself considered an SAE but should be followed up for congenital anomalies or birth defects.

Serious Adverse Reaction (SAR)

A serious adverse reaction is an SAE that is suspected as having a causal relationship to the trial treatment, as assessed by the investigator responsible for the care of the patient. A suspected causal relationship is defined as possibly, probably, or definitely related (see definitions of causality table).

Related Unexpected Serious Adverse Event

An adverse event that meets the definition of serious and is assessed by the CI or nominative representative as:

“Related” – that is, it resulted from administration of any of the research procedures, and

“Unexpected” – that is, the type of event is not listed in the protocol as an expected occurrence (see section 9.4))

Definitions of causality

Relationship	Description
Unrelated	There is no evidence of any causal relationship with the trial treatment
Unlikely	There is little evidence to suggest there is a causal relationship (e.g. the event did not occur within a reasonable time after administration of the trial treatment). There is another reasonable explanation for the event (e.g. the patient's clinical condition, other concomitant treatment)

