Acute lung toxicity is a specific consideration relevant to patients receiving radiotherapy to the IMC (expected to be 10-15% of recruited patients). As such, a powered subgroup analysis to evaluate this is planned. Based on RTOG assessment, the rate of $\geq G3$ pneumonitis occurring up to 3 months post-treatment in patients requiring radiotherapy to the IMC is anticipated to be 2% in the control group and we want to rule out an increase of 3% (to 5%) or more in the test groups. The two test groups will be combined for this analysis since the mean dose to the lung for both schedules is almost identical. Using an A'Hern single stage design with 90% power and a 5% one-sided significance level, 311 participants receiving IMC radiotherapy in either of the experimental arms would allow a rate $> 5\%$ to be ruled out. Rates of pneumonitis in control arm patients requiring IMC radiotherapy will be considered for the purpose of confirming the design assumptions but this will be a non-comparative analysis. If more than 9/311 cases of $\geq G3$ pneumonitis were reported in those receiving 5Fr SIB, then it would not be possible to exclude a rate of 5% or more.

Sample size for late normal tissue effects analysis.

Late normal tissue effects, and particularly breast induration, are important secondary endpoints of the trial. An analysis of clinician-assessed breast induration at 3 years is planned with the aim of demonstrating that there is not an unacceptable increase in risk of these symptoms associated with either of the test schedules. Based on IMPORT HIGH(6), we expect 11% of patients to have moderate/mark clinician-assessed breast induration by 3 years in the control group. A sample size of 823 patients per arm will provide 90% power to rule out an increase of 5% (to 16%) or more in either of the test groups (2.5% alpha for each pairwise comparison). This analysis will be based on the per protocol population. Allowing for approximately 20% of patients missing the relevant assessment data (or excluded from the per protocol population), the anticipated timing of this analysis is when 3090 patients have reached 3 years follow-up after randomisation.

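### The pneumonitis guideline describes its 311 patients in two ways and depends on one month-3 assessment, so a severe case lost before that visit need not count and any such loss leans towards safe

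*Protocol*

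**What the plan says.** **Event and design (section 10.1).** The event, based on RTOG assessment, is grade 3 or higher "pneumonitis occurring up to 3 months post-treatment in patients requiring radiotherapy to the IMC". The design is an "A'Hern single stage design with 90% power and a 5% one-sided significance level". The anticipated rate is 2%, and the stated aim is that "we want to rule out an increase of 3% (to 5%) or more in the test groups". The two test groups are pooled, giving 311 patients. More than 9 cases means that 5% cannot be excluded.

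**Denominator.** Section 10.4, under the timing of the analyses, describes the analysis as "including at least 311 patients receiving IMC radiotherapy in either test group with relevant 3-month RTOG data". Section 10.5, which holds the stopping guideline, counts cases among the first 311 IMC patients given the five-fraction schedule and does not require a 3-month record. It sets the trigger at 9 or more cases.

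**Sources of the event.** RTOG lung assessment is scheduled before treatment, at month 3 and at year 1 (sections 8.4, 8.6, 8.7 and 8.11). For month 3, section 8.6 says: "The following assessments should be conducted at 3 months after the start of radiotherapy for all participants". The lung assessment there may be done remotely. Section 9.1 begins its definition of a serious adverse event with "An SAE is any untoward medical occurrence that occurs after the first radiotherapy treatment and within 30 days of the last treatment of radiotherapy and", followed by the seriousness criteria; section 9.3 uses the same window. General adverse event reporting (section 9.2) applies to the early side-effects sub-study and ends at week 7.

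**Timing of the event.** Section 1.1 says that symptomatic pneumonitis peaks around 3 months after radiotherapy.

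**The concern.** The event is defined over an interval, but outside the SAE window it is observed at one visit. A patient who develops severe pneumonitis after SAE reporting has closed, and who dies or leaves follow-up before month 3, may have no RTOG grade on record. Under the section 10.4 description that patient can fall outside the 311. Under the section 10.5 description the patient is in the 311 but, with no RTOG grade, can sit there as a non-case. Both outcomes lower the observed rate.

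Patients lost this way would be among the worst cases, and the loss can act in one direction only. The rule turns on a count of 9 or 10. It informs the IDMC's recommendation, and section 10.4 intends the result for publication ahead of the primary endpoint as reassurance about safety.

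**Working it through.** **1. Reproduce the design.** Inputs from section 10.1: acceptable rate 2%, rate to exclude 5%, one-sided 5%, power 90%. Take the smallest n with some c such that P(X ≤ c | n, 0.05) ≤ 0.05 and P(X ≤ c | n, 0.02) ≥ 0.90, with X binomial.

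- The result is n = 311, c = 9: error 0.0497, power 0.9022. The plan's 311 and its cut-off of more than 9 are reproduced.
- With the section 10.5 trigger of 9 or more (c = 8), the error is 0.0252 and the power 0.8257. The two cut-offs disagree and need reconciling in their own right; results for both are shown below.

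**2. Locate the gap.** Five daily fractions end on day 5 of a Monday start, and 5 + 30 = day 35. Section 8.14 allows a start on any day; a course spanning one weekend ends on day 7, and 7 + 30 = day 37. From then until month 3 no lung assessment is scheduled and SAE reporting is closed. Sub-study patients have adverse event reporting to week 7 (day 49), which shortens the gap for them only. Recurrence and survival are first assessed at year 1.

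**3. Compare the two descriptions of the 311.** The three bullets in section 10.4 are parallel. In the other two the number is what remains after patients missing the relevant data or outside the per protocol set are removed:

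- skin: 345/3 = 115, and 115 × 0.90 = 103.5, against the stated 103;
- induration: 3090/3 = 1030, and 1030 × 0.80 = 824, against the stated 823.

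This favours reading 311 as a count of evaluable patients, but it does not prove it, because no missing-data allowance is given for pneumonitis. Section 10.5 has no data condition. Both readings are therefore carried forward.

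**4. Effect of losing cases.** Let p = 0.05 be the true rate and q the share of true cases with no month-3 record that are also not counted from elsewhere. The documents give no value for q; 5%, 10% and 20% are assumptions.

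- Section 10.4 reading (lost patient replaced by the next one with a record): observed rate = p(1 − q)/(1 − pq).
- Section 10.5 reading (patient stays in as a non-case): observed rate = p(1 − q).

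Probability of passing, that is, of wrongly excluding a true 5% rate, with n = 311:

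| q | Observed rate, 10.4 / 10.5 reading | Pass if ≤ 9, 10.4 / 10.5 reading | Pass if ≤ 8, 10.4 / 10.5 reading |
|---|---|---|---|
| 0 | 5.00% / 5.00% | 0.050 / 0.050 | 0.025 / 0.025 |
| 5% | 4.76% / 4.75% | 0.071 / 0.073 | 0.038 / 0.039 |
| 10% | 4.52% / 4.50% | 0.101 / 0.104 | 0.056 / 0.058 |
| 20% | 4.04% / 4.00% | 0.191 / 0.201 | 0.116 / 0.123 |

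The choice of reading barely changes the result.

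**5. What the shares mean in patients.** At 5%, 311 × 0.05 = 15.6 cases are expected. Shares of 5%, 10% and 20% are about 0.8, 1.6 and 3.1 lost cases.

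**6. A single lost case.** With 9 cases in 311 the one-sided 95% upper limit (exact) is 5.0%. If one further case had been lost and is restored, 10 in 312 gives 5.4%. The conclusion changes there, but would not change with a count well away from the cut-off.

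**The case against.** The section 10.4 line stands under a timing heading and says at least 311, so it can be read as a data-maturity trigger and not as a rule of exclusion. The guideline itself, in section 10.5, asks for no 3-month record. Section 10.4 leaves full definitions of the analysis sets to the SAP. The month-3 lung assessment may be remote, which covers most patients too ill to attend. Under section 8.10, patients who stop trial or routine follow-up still have data requested from routine visits or the medical record unless they withdraw consent for any further data, and section 8.9 keeps patients who discontinue treatment in follow-up. Deaths are collected, the IDMC reviews safety data at least annually, and it also weighs the control rate. If pneumonitis peaks near month 3, many cases will be visible at that visit. No figure in the documents supports any particular share of lost cases.

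Most of this stands. It shows that exclusion is not a stated rule and that the gap is narrow. It does not close the gap. Nothing says that pneumonitis found in the notes or on a death record counts towards a guideline based on RTOG assessment, and section 8.10 gives progression and death dates as its examples. A remote call does not reach a patient who has died. Nor is this only SAP detail: the protocol itself fixes the event, both descriptions of the 311, the cut-offs and the reporting windows, and an SAP cannot recover events that were never collected.

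**Conclusion.** The concern holds in a limited form. The protocol describes the 311 in two ways, and under either one a grade 3 or higher case between about day 36 and month 3, in a patient who dies or leaves follow-up before the visit, need not be counted. Any such loss biases the guideline towards safe. Remote assessment and medical-record follow-up narrow the gap without closing it.

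A reader might infer that the analysis counts only patients with a 3-month record and replaces the others, so that severe cases are removed by rule. The documents do not support that: the section 10.4 line may be a timing trigger, section 10.5 carries no data condition, and no replacement is described. A reader might also infer that one or two lost cases would generally reverse the IDMC's advice. That is true only near the cut-off, and the guideline is one input to that advice.

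The size rests on assumed shares. At 5% to 20% of cases lost, the chance of wrongly excluding a true 5% rate rises from 5.0% to between about 7% and 19-20% (pass if ≤ 9), or from 2.5% to between about 4% and 12% (pass if ≤ 8). The real share is unknown and probably small. Priority: should-fix, not must-fix.

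**What to change.** - Reconcile sections 10.1, 10.4 and 10.5 to one description of the 311, and reconcile the two cut-offs in the same edit.
- Define the event as any grade 3 or higher pneumonitis, grade 5 included, with onset from the start of radiotherapy to the month-3 time point. Count it from any source the trial already has: RTOG form, SAE form, death record or medical record.
- State that a patient with an event is evaluable whether or not the month-3 assessment took place. Require that record only to classify a patient as event-free.
- For IMC patients without a month-3 assessment, ask the site to confirm from the notes whether pneumonitis occurred. Section 8.10 already allows this unless consent for further data has been withdrawn.

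If every case is captured, the designed error is restored (0.0497 or 0.0252, depending on the cut-off). The cost is wording in three sections and one eCRF query for a small number of patients, with no new visit or procedure. The observed rate may be slightly higher, partly because cases would always be evaluable while non-cases without a record would not. That error is on the cautious side, and the query to sites keeps it small.

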9.4. Expected toxicities of radiotherapy

The following are expected toxicities of radiotherapy.

- Fatigue
- Skin changes
- Difficulty swallowing (for those who receive nodal radiotherapy)
- Pneumonitis
- Breast oedema
- Breast tenderness
- Breast shrinkage
- Breast hardening
- Breast lymphoedema
- Arm lymphoedema
- Rib fracture
- Lung fibrosis
- Ischaemia heart disease
- Telangiectasia

Clinical judgement should be exercised when considering the expectedness of events in relation to radiotherapy.

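### Per-time-point toxicity tests ignore the nodal-radiotherapy strata used in randomisation, so they are conservative for toxicities tied to nodal fields

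*Protocol*

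**What the plan says.** Protocol 10.2: "Allocation will be by computer generated random permuted blocks". The strata are surgery type (two levels), treating centre, and "need for nodal radiotherapy (none, nodes not including IMC or nodes including IMC").

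Protocol 10.4, on secondary endpoints: early and late toxicity frequencies at each time point are "compared between treatment groups using chi-squared test or Fisher's exact test as appropriate". No stratification is named. The next sentence adds longitudinal models and time-to-first-event analyses where suitable, "adjusting for balancing and other factors (for example, pre-treatment HADS score) where relevant". The same section promises adjustment of significance levels for multiple testing. On intervals it says "Event rates at key time points will be reported with 95% confidence intervals".

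Protocol 9.4 ties one expected toxicity directly to the nodal factor: "Difficulty swallowing (for those who receive nodal radiotherapy"). Section 10.3 lists oesophageal toxicity and arm lymphoedema among the secondary endpoints.

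**The concern.** Blocking within nodal strata makes the arms nearly equal in their share of nodal patients. If a toxicity occurs mostly in nodal patients, the variation between strata is largely removed from the difference between arms. A plain chi-squared or Fisher test still counts that variation as noise, so it rejects less often than its nominal level.

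In an efficacy comparison this would only be cautious. In a safety comparison it works against the patient: a true excess with a 1-week schedule is more likely to be reported as no difference. The multiplicity adjustment lowers the threshold further, and 10.4 intends to publish some toxicity results before the primary endpoint, to reassure readers about the safety of the 5-fraction approach. The loss is avoidable, because nodal need must be entered before a patient can be randomised (section 7).

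**Working it through.** **Inputs from the protocol.** Permuted blocks within surgery type, nodal need and centre (10.2). IMC patients 10-15% of recruitment (10.1). Lymphoedema in about 1 in 10 patients (1.1). Sub-study of about 345 patients, 103 per arm evaluable (10.1). At least 40 UK sites (5.2).

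**Inputs assumed.** Overall nodal share, toxicity rates by stratum, block size and number of sub-study sites. The protocol gives none of these, so ranges are shown.

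**The protocol's own figure first.** The one powered between-arm toxicity comparison is 3-year induration: control 11%, margin 5 points, one-sided 2.5%, power 90%.

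n = (1.960 + 1.282)² × 2 × 0.11 × 0.89 / 0.05² = 823 per arm, as stated. Then 3 × 823 / 0.8 = 3086, against 3090 stated.

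**Formula.** With stratum shares w and rates p, and overall rate P, the ratio of within-stratum to total variance is

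r = Σ w·p(1−p) / [P(1−P)].

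Under good balance, the true two-sided error of the plain test at nominal 5% is 2[1 − Φ(1.96/√r)].

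**Lymphoedema-like endpoint, worked case.** 60% without nodes at 3%, 40% nodal at 20%:
- P = 0.6 × 0.03 + 0.4 × 0.20 = 0.098, close to 1 in 10.
- Within-stratum variance = 0.6 × 0.0291 + 0.4 × 0.16 = 0.0815.
- Total variance = 0.098 × 0.902 = 0.0884.
- r = 0.92, and 1.96/√0.92 = 2.04, so the true error is about 4.1%.

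Simulation with the arms balanced within nodal stratum (1370 per arm) gave 4.1% for the plain test and 5.0% stratified. Power for a 25% relative difference was 63.5% against 66.0%.

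**Other assumed rates**, by stratum (none / nodes without IMC / nodes with IMC). Each range covers stratum shares of 60/27.5/12.5% and 45/40/15%.

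| Endpoint and rates | r | True error of plain test |
|---|---|---|
| Induration 10/12/14% | 0.998 | 4.98% |
| Grade ≥3 pneumonitis 0.2/0.5/2% | 0.993-0.994 | 4.92-4.93% |
| Arm lymphoedema 4/15/20% | 0.951-0.958 | 4.5% |
| Lymphoedema 2/20/25% | 0.894-0.914 | 3.8-4.0% |
| Any-grade swallowing difficulty 0/20/40% | 0.787-0.831 | 2.7-3.2% |

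**Check with actual blocking.** Incomplete blocks loosen the balance, so allocation was simulated within centre × surgery × nodal cells.
- Main trial, 4830 patients, 40 centres, blocks of 6, lymphoedema 4/15/20%: plain 4.3%, stratified 5.1% (Monte Carlo standard error about 0.5 points).
- Lymphoedema-like endpoint, blocks of 6, with missing data: plain 4.1%, stratified 5.5%; power 54% against 58%.
- Sub-study, 345 patients, 15 sites, blocks of 6, 10% missing, 40% nodal, rates 1% without and 40% with nodes: plain 3.1%, stratified 4.9%. Power for 40% against 18% in nodal patients was 50% against 58%. A separate run of an endpoint of this kind gave 3.0% and 4.9%, with power 49% against 56%.

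**The case against.** The case on the other side has several parts.

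- **It is analysis-plan detail.** Section 10.4 calls itself brief and defers full details. But it does name the test, and that test does not follow the design. Improving a stated method is different from asking for a missing one.
- **Adjusted toxicity models are already planned.** True, and nodal need is a balancing factor, so they offset part of the loss. They are conditional, however, and the protocol does not say whether they or the plain tests lead.
- **The plain test is valid.** Also true. It does not inflate type I error, so this is a point about efficiency.
- **Confidence intervals.** A reader might infer that intervals for arm differences will be too wide. The text does not support that: the toxicity intervals it promises are for event rates, and the named tests give p-values.
- **Oesophageal toxicity in the main trial.** Patient-reported oesophageal toxicity outside the sub-study is collected only in IMC patients (8.4, 8.6). That is a single nodal stratum, so there is nothing to remove. The oesophageal case is confined to the sub-study, whose powered skin analysis is itself non-comparative.
- **Size.** Perfect balance within nodal strata would give an error of about 2% for the sub-study case. That overstates it. Blocks run within small centre-level cells, and "Safety analyses will be based on a per protocol analysis set, according to treatment received", which loosens balance further. With 12 to 18 sites, block sizes of 3 to 9 and 10% missing, the error was 3.0 to 4.0%.
- **Powered analyses.** A reader might extend the point to the 3-year induration comparison or the primary endpoint. Neither is supported. For induration, r is at least 0.998 under the assumed rates, so 823 per arm barely moves. For recurrence, simulation at 2/4/6% by stratum gave 5.1% for both tests, and 10.4 already states "The primary analysis will be unadjusted, but estimates will also be presented after adjustment for factors used in the randomisation algorithm". The skin and pneumonitis rules are single-arm designs, and the pneumonitis rule lies wholly within IMC patients.

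**Conclusion.** The point holds as a minor matter of efficiency. For toxicities strongly tied to nodal fields, the plain per-time-point tests are conservative and give up some power to detect harm.

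The true two-sided error is about 4% for lymphoedema-like endpoints and about 3% for sub-study oesophageal-like endpoints, instead of 5%. The power loss is roughly 3 points (66.0 − 63.5 = 2.5; 58 − 54 = 4) and 7 to 8 points (56 − 49 = 7; 58 − 50 = 8) respectively.

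These sizes rest on assumed nodal shares, stratum rates, block size and site numbers. The direction needs only that nodal need predicts the toxicity. For rare toxicities, or those weakly related to nodal fields, the loss is negligible. No powered analysis, stopping guideline or primary conclusion changes.

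**What to change.** In Protocol 10.4, add one of two statements:

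1. Per-time-point between-group comparisons of toxicities related to nodal fields (arm lymphoedema, and oesophageal toxicity in the early side-effects sub-study) will use a Cochran-Mantel-Haenszel test, exact where cells are sparse, or a logistic model, stratified by nodal need as randomised.
2. The models adjusted for balancing factors are the main toxicity comparison, and the plain tests are descriptive.

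Leave the 3-year induration analysis and the primary Cox model as they are.

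The cost is wording only. Nodal need is already a required field at randomisation, so no data, patients or visits are added. Making the change before any comparative toxicity results are seen also settles which analysis leads.
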